The standard treatment for PJ is trimethoprim-sulfamethoxazole (TMP-SMX), an FDA approved, inexpensive antibiotic with a well-established safety profile. Despite the large body of evidence pointing toward PJ as a cause of COPD progression and a factor which leads to AECOPD, there has never been a trial of therapy for PJ in the COPD population. Such studies are difficult due to the invasive nature and low sensitivity of standard testing for PJ in this population. Using a highly sensitive PCR based assay, we can easily and safely test the sputum of COPD patients to identify carriers of PJ in order to include them in a clinical trial.

We hypothesize that adding TMP-SMX to standard of care treatment of AECOPD in patients who are colonized with PJ will improve the clinical outcome for the patient. **We further hypothesize** that TMP-SMX can eradicate colonization with PJ. This proposal seeks to confirm our hypothesis through the following two specific aims:

Aim 1: Determine if there is clinical improvement in COPD patients colonized with PJ treated with standard of care plus TMP-SMX vs standard of care plus placebo.

Rationale: For each participant we will determine time to return to baseline oxygen needs, need for mechanical ventilation during the index admission, length of stay, COPD assessment test, time to next admission for AECOPD and number of readmissions for AECOPD in the following 3 months.

Aim 2: Determine the persistence of colonization with PJ in AECOPD patients treated with standard of care plus TMP-SMX vs standard of care plus placebo.

2.1 Determine if TMP-SMX eliminates PJ at end of TMP-SMX therapy and the durability of clearance
2.2 Determine the duration of PJ colonization after standard of care treatment for AECOPD

Rationale: For each participant we will assay for the presence of PJ using PCR on sputum at end of therapy, 1 month and 3 months.

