We hypothesize that adding TMP-SMX to standard of care treatment of AECOPD in patients who are colonized with PJ will improve the clinical outcome for the patient. **We also hypothesize** that TMP-SMX will be able to microbiologically eradicate colonization with PJ in patients hospitalized with AECOPD.

Patients

Patients admitted with AECOPD are currently being identified daily for the EPIC study, IRB#2022-016, which is determining the prevalence of PJ colonization in our AECOPD patient population. This is accomplished using a search built in the EPIC EMR which identifies these patients. We will use the EPIC study to refer patients who are colonized with PJ to screening of inclusion/exclusion criteria for the TOPIC study (Table 1). To minimize potential for bias, the TOPIC study is randomized, double-blinded, and placebo controlled.

If eligible by inclusion/exclusion patients will be approached for consent for the TOPIC study, full consent will be used as this is an interventional study. If a potential patient is a woman of childbearing potential then a pregnancy test will be obtained to confirm that they are not pregnant (after consent since it will be a study procedure) and if positive the patient will be screen failed. See Appendix A for examples of specific exclusion criteria. Key personnel include

Inclusion	Exclusion

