
• Carries the diagnosis of COPD and admitted for and admitted with AECOPD to Beaumont, Royal Oak
• AECOPD requires increased cough, increased sputum production, and shortness of breath +/- increased oxygen needs from baseline• Able to produce a sputum sample• Men or women, age ≥40 and <90• Previously enrolled in the EPIC study and PJ detected in their sputum• Currently treated with steroids• Kidney function not severely impaired ($\text{CrCl} \geq 60$)• AST and ALT $\leq 5x$ Upper limit of normal• Willing and able to provide consent to the study	
• Currently diagnosed with pneumonia or COVID• Allergy or hypersensitivity to TMP-SMX• Current ICU admission or mechanical ventilation• Active cancer or chemotherapy (except non-melanoma skin cancer)• Other potentially confounding pulmonary diagnosis• HIV, leukopenia, neutropenia or other immunosuppressive condition or current use of immunosuppressive medications• Presence of gastrointestinal tract abnormalities that would prevent absorption of medications• Patients with concomitant infection requiring antibiotics active against PJ• Concomitant use of coumadin, phenytoin, pioglitazone, repaglinide, rosiglitazone, glipizide or gliburide• Megaloblastic anemia due to folate deficiency• Pregnancy• Expected life span less than 3 months

Table 1: Inclusion/Exclusion Criteria

3 attending physicians, 3 fellows, and 2 residents available to consent. In addition, a nurse coordinator experienced at consenting will be available to consent or assist the physicians with consenting in order to further educate physician trainees who are sub-investigators on this study. Given physician time commitments we expect the nurse may perform a majority of the consenting herself. Patients who consent for participation will be randomized in a 1:1 ratio to one of two groups.

Group #1 – Fifteen patients will receive a suspension with the equivalent of one DS TMP-SMX by mouth every 12 hours.

Group #2 – Fifteen patients will receive a suspension with placebo by mouth every 12 hours.

Randomization will be generated by biostats and sealed envelopes will be held by [name] in the Research Pharmacy to be opened when a patient is recruited. [name] is the only one who will be unblinded and, in case of an emergency, he can break the blind at the request of one of the attending physician investigators.

The Intervention

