Upon consent patients will be given the COPD Assessment Test (CAT) (<https://www.mdcalc.com/copd-assessment-test-cat>), a validated scoring system used in COPD patients to assess progression, functional status, and effectiveness of pulmonary rehabilitation.[29–32] Participants will be monitored daily while in the hospital for highest oxygen need, need for non-invasive or invasive mechanical ventilation, and adverse events, daily monitoring will be carried out by the nurse coordinator. Medications used for the treatment of COPD and antibiotics used will be collected retrospectively for each patient. If the patient remains hospitalized at end of therapy, 30 days, or 90 days then follow up will occur in the hospital. Otherwise, the patient will be asked to come to the Infectious Diseases Clinical Research Office for follow up visits at end of therapy (+0-3 days to allow for schedule issues and end of therapy falling on a weekend), 30 days +/- 5 days, and 90 days +/- 10 days. A \$30 stipend will be paid to the participants after each follow up visit. At the end of treatment visit, the medication diary will be collected. At each follow up visit, the nurse coordinator will review the patient's need for oxygen, their medications for the treatment of COPD, any need to see a physician or go to an urgent care or an emergency room for COPD, and any admission to the hospital for COPD. The CAT will be administered at each follow up visit. An expectorated sputum sample will be collected at each follow up visit which will be transported to the Infectious Diseases Research Laboratory for analysis; sputum samples will be processed and analyzed with the Unyvero LRT system for presence of PJ by PCR. The schedule of events for

[figure not shown]

Figure 1: Schedule of Events

the study is shown in figure 1.

Statistical analysis

No formal power analysis was performed, the sample size of 15 patients per arm is felt to be appropriate for a pilot study and appropriate to the funding for this application. We expect to find enough cases of PJ colonization to identify and recruit the 30 patients to be included in the study from the pool of patients for the EPIC study.

Time to return to baseline O2 requirements, and time to next admission for exacerbation will be analyzed using cox proportional hazards regression or other ~~more appropriate time~~ time-to-event analysis method. Need for mechanical

IRB APPROVAL DATE: 06/08/2022

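### Does the oxygen-recovery endpoint need a written rule for participants who are already at their usual oxygen level when randomised?

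*Combined protocol and SAP*

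**What the plan says.** Table 1 and the TOPIC Inclusion/Exclusion Checklist define an exacerbation in the same words: "AECOPD requires increased cough, increased sputum production, and shortness of breath +/- increased oxygen needs from baseline". The repetition shows that the optional oxygen criterion is intended. Participants must also be "Previously enrolled in the EPIC study and PJ detected in their sputum", and "Current ICU admission or mechanical ventilation" is an exclusion. The Patients section describes the route in: "We will use the EPIC study to refer patients who are colonized with PJ to screening of inclusion/exclusion criteria for the TOPIC study".

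The Aim 1 rationale under Specific Aims says: "For each participant we will determine time to return to baseline oxygen needs". Under Evaluations, "Participants will be monitored daily while in the hospital for highest oxygen need", and at each follow-up visit "the nurse coordinator will review the patient's need for oxygen". Under Statistical analysis: "Time to return to baseline O2 requirements, and time to next admission for exacerbation will be analyzed using cox proportional hazards regression or other"; the sentence ends by allowing a different time-to-event method.

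The visible text does not define baseline oxygen, the event or the time origin, and it does not say how to treat a participant with nothing to return from. The plan has 15 participants per arm, with a fallback of 10, no power calculation, and no primary endpoint named in the visible text.

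**The concern.** A participant can be at the usual oxygen level at randomisation in two ways. Oxygen need may never have risen, which Table 1 allows. Or it may have risen on admission and settled during EPIC enrolment, PCR testing, screening and consent. The ICU and ventilation exclusion also removes patients likely to have the highest need.

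For such a participant the endpoint has no natural value, and the possible codings give different answers. An event on day 0 adds tied events that carry no information about treatment, so a real effect is pulled towards 1. Keeping the participant at risk until some later censoring time also dilutes, and more so the later that time is. Censoring at time 0 removes the participant from every risk set.

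The outcome comes first in the list in the opening summary and in Aim 1, and the pilot is meant to inform a larger trial. An attenuated hazard ratio could mislead that planning, and a coding chosen after the results are seen could favour one arm.

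**Working it through.** **Inputs.** From the documents: 15 per arm, 1:1 allocation, oxygen need recorded by whole day in hospital, follow-up to 90 days, fallback of 10 per arm. Assumed, because the documents give no figures: a share *f* already at baseline of 5% to 50%, independent of arm; a true hazard ratio (HR) of 2 among the rest (above 1 means faster return on TMP-SMX); exponential return times with a placebo median of 4 days, rounded up to whole days.

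**Reference point.** The plan states no power, HR or event count, so there is no figure of its own to reproduce. With nobody at baseline and 30 events, power = Φ(ln 2 × √30 / 2 − 1.96) = Φ(1.898 − 1.960) = 0.475. Simulation (2,000 trials) gives 0.43.

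**Dilution under day-0 coding.** Roughly, a fraction *f* of the events has log HR 0 and the remaining 1 − *f* has log HR ln 2, so the averaged HR is about 2^(1−f). The simulated columns come from 6,000 trials per setting (Cox model with Efron ties, two-sided 5% score test).

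| Share at baseline | 2^(1−f) | Median HR, day-0 event | Median HR, restricted | Power, day-0 | Power, restricted |
|---|---|---|---|---|---|
| 5% | 1.93 | 1.95 | 2.04 | 0.40 | 0.42 |
| 10% | 1.87 | 1.87 | 2.02 | 0.35 | 0.40 |
| 20% | 1.74 | 1.70 | 2.01 | 0.27 | 0.35 |
| 30% | 1.62 | 1.58 | 2.00 | 0.20 | 0.30 |
| 50% | 1.41 | 1.37 | 2.06 | 0.11 | 0.23 |

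A check with 500 per arm gives 1.73, 1.60 and 1.38 at 20%, 30% and 50%, so the dilution is systematic. With 10 per arm at 20% it is 1.74 against 2.05. With no true effect, both codings centre on 1.00.

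The restricted column is also the result of censoring at time 0. The first possible event falls on day 1, so a participant censored at 0 never enters a risk set.

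**Bias and noise together.** Root mean squared error of the log HR is √(bias² + SD²), with bias taken from the median HR:

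- 20%, day-0: bias = ln(2/1.70) = 0.163, SD 0.41; √(0.163² + 0.41²) = 0.44. Restricted: bias ln(2.01/2) = 0.005, SD 0.49; error 0.49.
- 50%, day-0: bias = ln(2/1.37) = 0.378, SD 0.39; √(0.378² + 0.39²) = 0.54. Restricted: bias ln(2.06/2) = 0.030, SD 0.67; error 0.67.

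So restriction removes the bias and keeps more power, but its estimate has the larger total error. Part of the day-0 advantage is plain shrinkage towards 1, so this does not make day-0 coding preferable. It shows that at 15 per arm sampling noise is at least as large as the bias, even at 50%. In a single trial at 20%, the day-0 estimate lies further from 1 than the restricted one 24% of the time.

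**Choosing after the fact.** With no effect and 20% at baseline, taking the better of the two codings gives 8.8% false positives, against 5.9% and 6.4% for each alone: an excess of 8.8 − 6.4 = 2.4 percentage points over the higher one.

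**How large could the share be?** Even if every patient had a raised need on admission, the share back at baseline by randomisation would be 1 − 2^(−lag/median). With a 4-day median and lags of 1, 2 and 3 days that is 16%, 29% and 41%. Both inputs are assumed. The Resources section describes enough assay capacity to avoid overnight storage on all but the busiest days, which points to a short testing lag. The number who never had a raised need cannot be derived from the documents.

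**The case for a change.** The best case for a change is that the gap is in the visible text and is cheap to close. The optional criterion appears twice, Aim 1 refers to each participant, and the statistical section has no at-risk rule. The dilution is real and reproducible. Restricting on a pre-randomisation characteristic preserves the randomised comparison and would take one sentence. A pilot that feeds a larger trial should not leave its first-listed outcome open to several codings, which at 20% disagree on p < 0.05 in 16% of simulated trials.

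The omission and the direction of the effect stand. The harm does not follow from the plan, because it needs a coding that the plan never states. The Aim 1 phrase says what is measured on each person; it does not define an analysis set, and the Statistical analysis section does not say that all 30 enter this model. That section also leaves the time-to-event method open.

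The fear of a convenient choice is limited as well. The trial is double-blind, and the plan says that only the envelope holder in the Research Pharmacy is unblinded, so the convention can be settled before unblinding. Whether usual oxygen need is already recorded cannot be judged, because Figure 1 and the EPIC forms are not available. Competing-risk models, interval censoring and sustained-return rules are debatable choices for 20 to 30 patients and are not needed to settle this point.

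**Conclusion.** The concern identifies an unwritten definition, not an error. On the ordinary meaning of the endpoint, someone who is not above the usual oxygen level has nothing to return from and does not contribute to the risk set; on that reading the dilution does not arise. Under the less natural day-0 coding, the median HR would fall from about 2.0 to 1.7 if 20% were at baseline, and the difference would be negligible at 5%. Those sizes rest wholly on the assumed share, true HR and recovery time, none of which the documents give. The restricted analysis has its own price: fewer than 30 patients (24 on average at 20%) and a wider interval.

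No stated power, threshold or primary endpoint changes under either coding, and the section on potential problem areas already concedes that differences may not reach significance. The analyst can be expected to state the at-risk set and time origin when reporting, with the number already at baseline in each arm. That is normal practice and does not require a change to the plan.

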Multiple studies have confirmed high rates of PJ colonization in COPD patients, and the highest rates are seen in patients with AECOPD.[20] During the clinical trial of the Unyvero system for lower respiratory infections at Beaumont, we found 8 patients out of nearly 500 total patients in the study who were positive for PJ. Of note, HIV patients, who are at the highest risk for PJP, were excluded from that study. Two of the 8 patients had other classic risk factors for PJ pneumonia (transplant and leukemia), the remaining 6 patients all had severe COPD and two of them were so severe that they entered hospice. These findings were what led us to conclude that the association of PJ with COPD was clinically significant and led to the design of this trial.

Through this study we hypothesize that we will be able to show that the simple addition of TMP-SMX to the standard treatment regimen for AECOPD will lead to clinical benefit. If our hypothesis is confirmed larger trials of therapy designed to treat AECOPD and to prevent acceleration of the disease process would be possible. TMP-SMX is a proven, safe, and inexpensive antibiotic, the addition of TMP-SMX as a treatment for AECOPD would be both safe and cost-effective. More importantly, using the paradigm of AIDS patients, prophylaxis with a single daily tablet of TMP-SMX can nearly eliminate the incidence of PJ pneumonia.[24] Further clinical trials could compare if daily TMP-SMX could significantly reduce AECOPD. A reduction in AECOPD of even 5% would represent a huge improvement in clinical care and significant savings to the cost of healthcare.[25]

The low cost, safety profile, and ease of availability of TMP-SMX makes this a therapy that could be applied worldwide even in the lowest resource areas.

Innovation

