The typical treatment of PJ pneumonia is TMP-SMX is 2 DS tablets every 8 hours for 21 days. Higher concentrations of TMP-SMX are needed to treat the cyst form found in PJ pneumonia. For colonized patients who carry the vegetative form of PJ, a standard dose of TMP-SMX is more appropriate and less likely to cause side effects and potential discontinuation. As such the dose to be used for this study is 1 DS Q12H for 10 days. TMP-SMX is a large tablet which is difficult to over-encapsulate for blinding purposes. As such, the Research Pharmacy will supply a TMP-SMX suspension in individual dose syringes or a matching placebo in individual dose syringes for this study. A single syringe for TMP-SMX will contain 160 mg of trimethoprim and 800 mg of sulfamethoxazole, the same amount found in one DS tablet of TMP-SMX. If the patient is discharged prior to completing the 10-day course of the medication, they will be sent home with the remaining days of study medication and a medication diary which ~~IRB NUMBER: 2022-02~~ ~~IRB NUMBER: 2022-02~~ will be collected at the end of therapy visit. Standard operating

procedures used for all clinical trials within the Infectious Diseases Clinical Trials Unit will be followed at discharge including appropriate instruction of the patient on medication use, filling out the medication diary, when to contact the study staff, and making appointments for follow up.

When a patient with PJ pneumonia is hypoxic, the treatment of the PJ in addition to TMP-SMX includes steroids. This is done to minimize the inflammation from the β -D-glucans of PJ that are released when PJ is killed by TMP-SMX. It is unclear if steroids would be needed with the lower expected levels of PJ in the AECOPD patients but, since most patients with AECOPD are treated with steroids in any case, we feel it is safer to only include patients receiving steroids, hence the inclusion requirement of steroid use.

Evaluations

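### The visible text covers adverse events only during the hospital stay and plans no adverse-event comparison, though dosing may continue at home and early withdrawals are removed

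*Combined protocol and SAP*

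**What the plan says.** The only mention of adverse-event collection in the visible text is under Evaluations: "Participants will be monitored daily while in the hospital for highest oxygen need, need for non-invasive or invasive mechanical ventilation, and adverse events". The nurse coordinator does this daily monitoring.

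The Intervention (Study design) sets the length of treatment: "As such the dose to be used for this study is 1 DS Q12H for 10 days". For patients discharged before the course is complete, "they will be sent home with the remaining days of study medication and a medication diary". Discharge follows the unit's standard operating procedures, which include "appropriate instruction of the patient on medication use, filling out the medication diary, when to contact the study staff, and making appointments for follow up".

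Visits are planned at end of therapy (0 to 3 days after), day 30 (±5) and day 90 (±10). At each of them "the nurse coordinator will review the patient's need for oxygen, their medications for the treatment of COPD", together with physician, urgent-care and emergency-room contact for COPD and "any admission to the hospital for COPD". The visits also include the COPD Assessment Test (CAT) and a sputum sample, and the medication diary is collected at end of treatment.

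The Statistical analysis section covers recovery of baseline oxygen, time to next admission, mechanical ventilation, length of stay, urgent-care and emergency visits, AECOPD hospitalisations, mortality, durability of decolonisation, change in COPD medications and CAT. It also says that participants who withdraw before the EOT assessment are removed from the study and replaced, without regard to the reason.

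**The concern.** Study drug may be taken outside the setting in which the text places adverse-event monitoring. The questions listed for the later visits would not bring out a non-COPD harm. A patient who saw a doctor or was admitted for a drug reaction during home dosing could answer every listed question truthfully and leave no record of it. Events that are recorded in hospital have no planned tabulation, and the withdrawal rule takes out the patients whose tolerability is most informative.

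The protocol itself treats tolerability as relevant. The Intervention section justifies the regimen partly by fewer side effects and less discontinuation. Clinical Relevance says that "the addition of TMP-SMX as a treatment for AECOPD would be both safe and cost-effective". The study is meant to support larger treatment and prophylaxis trials. If harms are sought less after discharge and early withdrawals are not counted, the by-arm picture those trials inherit would lean towards no harm.

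**Working it through.** This is mainly a comparison of texts. The plan states no safety figure to reproduce.

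**1. Where adverse events are sought.** In hospital, the text names them. After discharge, the visit list has oxygen need, COPD medications, care contacts, admissions, CAT, sputum and diary. Adverse events are not on it. The admission item is explicitly for COPD. For physician, urgent-care and emergency contacts, the COPD qualifier comes at the end of the phrase. It most naturally covers all three, but it could attach to the last alone.

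**2. What is analysed.** Of the outcomes listed, mortality is clearly a safety outcome. Mechanical ventilation bears on safety but is listed as a clinical outcome of the exacerbation. Nothing covers adverse events, serious events or stopping study drug, and no safety population is defined.

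**3. How much dosing may fall at home.** Doses in the course: 10 days × 2 per day = 20. Home share = (10 − d)/10, where d is the number of inpatient dosing days. The documents give no length of stay, so d is assumed:
- d = 2: 8/10 = 80%, or 16 doses
- d = 7: 3/10 = 30%, or 6 doses
- d = 10: none

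This is the share of dosing outside the stated monitoring. It is not a share of events missed, because an EOT visit follows the course.

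**4. What incomplete capture would do.** Let p be the true event rate on active drug and f the share of events captured (both assumed). The chance of recording at least one event in n patients is 1 − (1 − p·f)^n. With p = 10% and n = 15:
- f = 100%: 1 − 0.90^15 = 79%
- f = 50%: 1 − 0.95^15 = 54%
- f = 30%: 1 − 0.97^15 = 37%

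At the fallback of 10 per arm (Potential problem areas and alternative tactics), full capture gives 1 − 0.90^10 = 65% and 30% capture gives 1 − 0.97^10 = 26%.

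**5. What the withdrawal rule would do.** Suppose w treated patients withdraw before EOT because of a reaction and each is replaced in the same arm (an assumption, since the text does not say how replacements are allocated). Then 15 + w patients were exposed, but the 15 analysed contain none of those w events. For w = 1 the hidden proportion is 1/16 = 6.3%. For w = 2 it is 2/17 = 11.8%. Patients who stop the drug but stay in the study are not affected.

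**The case against.** The strongest reply is that the recording gap may lie in what can be seen and not in the plan. Evaluations refers to Figure 1 for the schedule of events, the figure is not available here, and such a schedule is where visit-by-visit adverse-event collection would normally appear. The sentence on daily inpatient monitoring also does not say that collection stops at discharge. This stands as a limit: a reader might infer that adverse events are collected only in hospital and that harm at home would go largely unrecorded, but the documents do not establish that. What they show is that the prose names adverse events for the hospital stay alone.

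There are also other routes. Patients are told when to contact staff, unit procedures apply, and a diary is collected at a visit soon after the course ends. These allow passive reporting. However, no adverse-event content is described for any of them, and the diary is described as a medication diary.

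It would also be too strong to say that no safety comparison is listed, because mortality is analysed. Mortality does not capture tolerability, so the narrower statement holds.

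The magnitude can be challenged too. The home share depends wholly on an assumed stay. A reader might also point to the two-sided 95% upper bound for 0 events in 15, 1 − 0.025^(1/15) = 21.8% (30.8% for 0 in 10), as a measure of the defect. It is not: it reflects sample size and would be the same after the fix.

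Finally, neither specific aim concerns safety, and the protocol rests safety on the drug's established record. That lowers the stakes. It does not remove the case for describing tolerability by arm in a placebo-controlled trial that presents itself as the first in this population.

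**Conclusion.** The concern holds in a limited form. The visible prose provides for adverse-event monitoring only in hospital, and the itemised follow-up review omits adverse events and, on its natural reading, non-COPD contacts. Whether that is a gap in the plan or only in its wording depends on Figure 1.

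The analysis gap does not depend on the figure. No comparison of adverse events, serious events or discontinuations is listed, and removing and replacing early withdrawals would take out patients who leave because of a reaction.

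The size cannot be fixed from the documents. The home share of dosing is 30% to 80% if 2 to 7 inpatient dosing days are assumed, and zero for a 10-day stay. The capture calculation shows the direction and possible scale of the loss under assumed rates; it does not estimate how many events would be missed. The change should be made because it is cheap and because events not asked about cannot be fully recovered later.

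**What to change.** In Evaluations, add two items to the review at the visits already scheduled: adverse events, and physician, urgent-care, emergency-room and hospital contacts for any reason. State that serious events are collected through day 90. If Figure 1 already lists adverse events at visits, align the text with it.

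In Statistical analysis, add one descriptive table by arm of adverse events, serious events and study-drug discontinuations, with exact confidence intervals, in everyone who took at least one dose. State that participants who withdraw before EOT stay in this table even if they are replaced for the efficacy analysis. That sentence is needed because the current rule would otherwise conflict with the table.

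The cost is a little extra nurse time and one table. Sample size and visit schedule do not change. With 10 to 15 patients per arm the result is descriptive and should not be presented as a powered test.

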By identifying patients colonized with PJ in the EPIC study, we will carry the cost of screening for the TOPIC study in the EPIC study, which allows the funding for this study to bear other needed expenses and make it feasible. The key personnel for the EPIC study overlap completely with the TOPIC study. We aim to enroll 30 patients but if we will have difficulties in recruiting, we may need to decrease the number of patients in the treatment group to 10 in each arm. Having a stipend for follow up visits will help with recruitment as will having [name], the director of Pulmonary Rehabilitation, as an investigator.

It is possible that we may see clinical improvement in the TMP-SMX group without microbiologic eradication. This could be due to TMP-SMX incompletely killing the PJ, we could have chosen a sub-optimal dose for the study, or it could be that the high sensitivity of PCR and the ability to detect dead organisms will work against us and we could still detect the organisms even if all were killed. Checking for colonization again at 30 days and at 90 days may be able to reveal this as dead organisms are cleared from the respiratory tract. It may be that it will take a longer trial to actually show microbiologic clearance even in the setting of clinical benefit.

This is a pilot study and, since we will have a small number of patients, we may not be able to detect statistically significant differences between the two groups, however by selecting the known PJ colonized patients for the study we are increasing the chances of being able to show a difference between the groups.

Potential for continuing this study with additional extramural funding

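### The analysis of time to return to baseline oxygen names no covariate; prespecifying the entry oxygen gap would correct chance imbalance and, if the gap is prognostic, recover precision

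*Combined protocol and SAP*

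**What the plan says.** All references are to the combined protocol and SAP.

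- **Analysis (Statistical analysis).** "Time to return to baseline O2 requirements, and time to next admission for exacerbation will be analyzed using cox proportional hazards regression", or by another time-to-event method. No model terms are listed for this outcome, and no covariate is named for any other.
- **Allocation (Patients).** "Patients who consent for participation will be randomized in a 1:1 ratio to one of two groups". On the list itself, the text says "Randomization will be generated by biostats and sealed envelopes will be held by" the Research Pharmacy. No stratification factor is described.
- **Size (Statistical analysis; Potential problem areas and alternative tactics).** "No formal power analysis was performed, the sample size of 15 patients per arm is felt to be appropriate for a pilot study". If recruitment is slow, "we may need to decrease the number of patients in the treatment group to 10 in each arm".
- **Oxygen data (Evaluations).** Patients are "monitored daily while in the hospital for highest oxygen need"; after discharge, oxygen need is reviewed at the follow-up visits.
- **Eligibility (Table 1).** The exacerbation must include "shortness of breath +/- increased oxygen needs from baseline".

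Time to return to baseline oxygen is the first outcome listed under Aim 1. The text designates no primary outcome.

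**The concern.** I read baseline as the patient's usual oxygen need before the exacerbation, which is how Table 1 uses the word. The endpoint is then the time to close the gap between current and usual need. Because Table 1 does not require raised oxygen needs, patients can enter with a large gap, a small one or none. A link between entry gap and recovery time is therefore plausible from the definition of the endpoint.

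If the analysis is run by arm alone, two things follow. Chance imbalance in the entry gap, which is common at 10 to 15 per arm, feeds straight into the estimated effect. And if the gap is prognostic, leaving it out of a Cox model moves the hazard ratio towards 1 and costs precision. This matters even in a pilot, because the section on extramural funding makes the design of a larger trial depend on whether this one shows potential clinical improvement.

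**Working it through.** **The plan's own figure.** There is none to reproduce: the plan gives no alpha, effect size, target power or event count. Everything below marked as assumed is mine.

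**Inputs from the documents.** 15 per arm, fallback 10; 1:1 allocation; Cox regression; entry gap variable and possibly zero.

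**Inputs assumed.** Two-sided alpha 0.05; conditional hazard ratio (HR) for recovery of 1, 2 or 3; 10% of patients censored; log HR per SD of gap of 0, 0.5, 1.0 or 1.5.

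**Step 1: reference power.** Schoenfeld: power = Φ(√(d/4)·ln HR − 1.96), with d events.
- d = 30, HR 2: √7.5 × 0.693 − 1.96 = −0.06, so 47.5%.
- d = 20, HR 2: √5 × 0.693 − 1.96 = −0.41, so 34%.
- 80% power at HR 2 needs 66 events.

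**Step 2: chance imbalance.** The between-arm difference in the standardised gap has SD √(2/n per arm).
- 15 per arm: √(2/15) = 0.365; the chance of a difference above 0.5 SD in either direction is 17%.
- 10 per arm: √(2/10) = 0.447; the chance is 26%.

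**Step 3: simulation.** 8,000 trials per setting, exponential times, standard-normal gap, every patient at risk, likelihood-ratio test. Entries are power (%) for arm alone v arm plus gap.

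| Log HR per SD of gap | HR 2, 15 per arm | HR 3, 15 per arm | HR 2, 10 per arm |
|---|---|---|---|
| 0 | 40 v 40 | 75 v 75 | 28 v 28 |
| 0.5 | 31 v 39 | 63 v 74 | 23 v 27 |
| 1.0 | 21 v 39 | 43 v 73 | 16 v 27 |
| 1.5 | 15 v 37 | 29 v 71 | 12 v 25 |

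Simulation standard error is about √(0.4 × 0.6/8000) = 0.5 points at 40%. When the gap does not predict recovery, adjustment costs at most 0.6 points (for example 75.1% to 74.5% at HR 3, 15 per arm).

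**Step 4: the estimate** (15 per arm, true HR 2, log HR 1.0 per SD).
- Median estimated HR is 1.61 with arm alone and 2.08 adjusted.
- The arm-alone log HR moves by about 0.70 per SD of imbalance; the adjusted one by about 0. A one-SD chance imbalance therefore shifts the arm-alone estimate by 0.70 × 0.365 = 0.26, a factor of e^0.26 = 1.3.
- The arm-alone test rejects in 3% of trials where imbalance exceeds 0.5 SD against the active arm, and in 59% where it exceeds 0.5 SD in its favour.

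**Step 5: Type I error** (HR 1).

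| | Arm alone | Arm plus gap |
|---|---|---|
| 15 per arm | 5.1–6.0% | 5.5–6.8% |
| 10 per arm | 5.7–6.1% | 6.4–7.3% |

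The adjusted likelihood-ratio test is mildly liberal, more so at 10 per arm. At 15 per arm and log HR 1.0 per SD the two tests are close (5.8% v 6.0%), so this does not explain the power difference there.

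**Step 6: zero-gap patients.** The simulation has none, but Table 1 allows them. They are already at baseline on entry and have no return to time. If 20% or 40% of 30 patients have no gap (assumed), at most 24 or 18 can have an event, and Schoenfeld power at HR 2 falls from 47.5% to 40% or 31%. Also, log(gap) is undefined for them.

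**The case against.** The strongest reply is that this is a pilot with no power calculation, which itself concedes that it may miss differences; there is no power target to fall short of, and an analysis by arm alone is valid under randomisation. That stands. It limits the point to precision and to chance imbalance in the estimate. Part of the attenuation is also non-collapsibility: the adjusted model estimates a conditional hazard ratio, so the lower unadjusted value is not simply an error.

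Four stronger readings are tempting, and the documents support none of them.

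- *A reader might infer that the plan commits to a model with arm alone and to unstratified randomisation.* It is silent on both, and it leaves the choice of time-to-event method open.
- *A reader might infer that the entry gap largely determines recovery time.* That is plausible from the endpoint's definition, but no figure in the documents measures it. The gain could be nil.
- *A reader might infer that the covariate is already recorded.* The text provides for the daily highest need in hospital, and the endpoint cannot be computed without the usual need. It names no value at randomisation, and the schedule figure is not available here. The day-1 maximum may fall after the first dose, in which case it is not a baseline value.
- *A reader might infer that adjustment is free of side effects.* The adjusted likelihood-ratio test is slightly liberal at these sizes.

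Silence still needs filling. Choosing covariates after seeing 20 to 30 patients' results would invite doubt about selection.

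**Conclusion.** The point holds as an improvement in efficiency and in handling imbalance, not as the correction of an invalid test. At an assumed conditional HR of 2 and 15 per arm, the gain in power from adjusting runs from none to 22 points (15% to 37%); at HR 3 it reaches 42 points (29% to 71%). Where in that range the trial lies depends on the gap's prognostic strength, which is assumed. The size of chance imbalance does not depend on that assumption: a 17% chance (26% at 10 per arm) of a difference above 0.5 SD. Its effect on the estimate does. The figures also assume exponential times, 10% censoring and no zero-gap patients.

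The point covers the oxygen outcome only, not time to next admission. Adjustment does not deal with the separate fact that oxygen need after discharge is seen only at visits, so return times there are interval-censored.

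**What to change.** Before unblinding, specify in the Statistical analysis section:

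1. Cox regression of time to return to baseline oxygen on arm plus the entry oxygen gap, defined as the last recorded need before first dose minus the usual requirement, in a stated unit. Enter it as one continuous covariate, linear or log(gap + 1), with the scale fixed in advance; do not use log(gap).
2. Patients with zero gap at entry are not at risk for this endpoint and are reported separately by arm.
3. The p-value comes from a permutation test that follows the actual randomisation scheme, or from another small-sample method.
4. The unadjusted result is reported as supportive.

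The cost is one degree of freedom, a little more analysis work, and making sure that the case report form captures a pre-dose oxygen value and the usual requirement. No extra visit is needed.
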